8. STUDY PROCEDURES

Pictures of the study procedures are outlined in appendix A and an outline of study procedures in relation to study visits is outlined in appendix B.

Nasal lavage: 10ml of normal saline will be administered and collected gently through a disposable plastic olive-shaped device into both nostrils prior to each challenge. This acts to “clean” the nasal mucosa of nasal debris prior to challenge and the nasal washing will be discarded.

Nasosorption: Nasal mucosal lining fluid will be collected non-invasively using nasosorption initially regularly (0min, 15min, 30min, 1h, 2h) then at two-hourly intervals (4h, 6h, 8h, 24h) after each challenge to assess the kinetics of interferon, cytokine and chemokine production.

Nasal mucosal epithelium: Nasal mucosal epithelial cells will be collected at the screening visit, baseline (0h) and 24 hours after each challenge to assess transcriptional and epigenetic signatures and to culture epithelial cells in the lab. Therefore, a maximum of up to three sets of samples per volunteer will be taken from half of the group undergoing single challenge (n=12), whilst the remainder of the group undergoing double challenge will have a total of five sets of samples taken (n=12). Up to five sets of nasal curettage samples were taken per volunteer in a prior study using R848 with good tolerability and no withdrawal of participants from the study¹⁵. Topical anaesthetic spray may be offered prior to procedures.

- **Nasal brushings** are taken using a small cytology brush from the nasal inferior turbinate – up to two samples will be taken (one from each nostril).
- **Nasal curettage** involves the use of a small plastic curette to gently “scrape” a small amount of tissue from the nasal inferior turbinate – up to four samples will be taken (two from each nostril).

Post-nasal space biopsy will be an optional procedure in order to obtain a small sample of tissue (0.5cm) taken from the postnasal space using endoscope and forceps under topical local anaesthetic. It will be performed by a trained Ear, Nose and Throat (ENT) surgeon ([name]) in a specific area of Addenbrookes hospital with dedicated facilities for the procedure. The purpose of this is to obtain a larger and deeper volume of tissue than the nasal curettage/brushings to facilitate detailed molecular phenotyping particularly of immune cell subsets, which are found underneath the epithelial layer. The procedure is generally well tolerated, and complications are rare. This procedure is more invasive than performing nasal curettage/brushings and will therefore only be performed twice in up to 12 people. These participants will only undergo a single nasal challenge and not the second repeat challenge. Volunteers who agree to have the procedure will have the first sample collected at the screening visit. There will then be a minimum of 6-weeks (to ensure wound healing) before performing nasal challenge with saline (up to n=2) or R848 (up to n=10), and a subsequent post-nasal space biopsy performed 24 hours after challenge.

Blood: Blood will be collected on the following occasions:

- Screening visit for routine safety and eligibility (9ml) and DNA analysis (8.5ml)
- Before (0h) and after (24h) each nasal challenge for single cell analysis and Truculture (13ml each time-point)
- Before (0h) and twice after (4h, 24h) nasal challenge for serum and full blood count (9ml each time point).

This means that half of the volunteers undergoing single challenge (n=12) will provide a total of approximately 70ml blood over three visits and the remaining half undergoing 2 challenges (n=12) will provide a total of approximately 125ml blood over five visits.

8.1 Informed Consent

The participant must personally sign and date the latest approved version of the informed consent form before any study specific procedures are performed.

Written and verbal versions of the participant information and Informed consent will be presented to the participants detailing no less than: the exact nature of the study; the implications and constraints of the protocol; the known side effects and any risks involved in taking part. It will be clearly stated that the participant is free to withdraw from the study at any time for any reason without prejudice to future care, and with no obligation to give the reason for withdrawal.

The participant will be allowed as much time as wished to consider the information, and the opportunity to question the Investigator, their GP or other independent parties to decide whether they will participate in the study. Written Informed Consent will then be obtained by means of participant dated signature and dated signature of the person who presented and obtained the informed consent. The person who obtained the consent must be suitably qualified and experienced and have been authorised to do so by the Chief/Principal Investigator as detailed on the Delegation of Authority and Signature log for the study. The original signed form will be retained at the study site within the Trial Master File (TMF) or Investigator Site File (ISF). A copy of the signed Informed Consent will be given to participants and a copy retained in the participant medical notes.

8.2 Screening and Eligibility Assessment

Participants in this study will be recruited from Cambridge University Hospital (CUHFT), University of Cambridge, volunteer databases and advertising in the Cambridge area. Participants from CUHFT may be recruited from outpatients (in particular departments of allergy and asthma) or comprise of staff working there. Employees or students at the University of Cambridge who express an interest in taking part are also eligible. Advertisements for the study will be through organisational poster. Pre-screening of interested potential participants will involve telephone screening and if potentially eligible they will receive the participant information sheet and consent form by email at least 24 hours prior to the screening visit.

A comprehensive screening visit will be undertaken at the CCRC to evaluate the following:

Demographics: date of birth, gender, race, smoking and drinking habits

Medical History: Details of any history of disease or surgical interventions and a systems review to determine inclusion/exclusion criteria

Concomitant Medication: All over-the-counter or prescription medication, vitamins, and/or herbal supplements will be recorded on CRFs.

Physical Examination as well as physiological observations, height, weight and oral temperature will be recorded.

ECG Test: A 12-lead ECG will be taken for each participant. At least the following ECG parameters will be recorded: heart rate (HR), PR, QT and QRS intervals and QT_c. The report will be signed by the Investigator who will record in the CRF whether it is normal, abnormal but not clinically significant, or abnormal AND clinically significant. In the latter case the eligibility of the participants will be reviewed.

Laboratory Tests: Biochemistry, full blood count, liver function test, total IgE, skin prick allergy testing, pregnancy test (for women) will be performed.

COVID Testing: All participants will be required to be free of any potential symptoms of COVID (fever, cough, anosmia) for at least 14 days prior to enrolment and not have any history of long-term symptoms due to COVID. A negative SARS-CoV-2 lateral flow or PCR test will be required prior to nasal sampling procedures. Staff and students from the University of

Cambridge as well as staff from CUHFT who are undergoing routine surveillance screening for COVID-19 and who test negative for the disease will also be invited to participate in the study.

All laboratory results will be reviewed by the Investigator who will record in the CRF whether they are normal, abnormal but not clinically significant, or abnormal AND clinically significant. In the latter case the eligibility of the participants will be reviewed.

Nasal curettage and brushings: This will be collected from all volunteers

Post-nasal space biopsy: For up to half the group (n=12) who volunteer for post-nasal space biopsies to be collected, a negative COVID test is required prior to sampling. These participants will undergo nasal challenge experiments a minimum of 6-weeks after the biopsy to allow for adequate time for wound healing.

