6.2 Primary Outcome Measure

1. Increase in CXCL10 nasal mucosal gene expression at 24 hours after nasal challenge with R848 compared to baseline

Secondary Outcome Measures

1. Difference in CXCL10 nasal mucosal gene expression at 24 hours after R848 challenge between healthy subjects and those with allergic rhinitis
2. Change in participant's temperature between first and second nasal challenge with R848 (as a marker of clinical tolerability)
3. Difference in CXCL10 nasal mucosal protein in nasal mucosal lining fluid over 24 hours expressed as area under curve (AUC) between first and second nasal challenge with R848.

Exploratory Outcome Measures

1. Difference in CXCL10 after ex-vivo stimulation of blood samples with LPS before and 24 hours after nasal challenge with R848
2. Single-cell gene expression and epigenetic profiles in mucosal tissue and blood before and after nasal challenge with R848
3. Comparison of single-cell and epigenetic profiles between healthy and allergic disease groups

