7.2 Inclusion Criteria

- Participant is willing and able to give informed consent for participation in the study.
- Male or female aged 18 years and above
- Able (in the Investigators opinion) and willing to comply with all study requirements.
- Willing to allow his or her General Practitioner and consultant, if appropriate, to be notified of participation in the study.
- Female participants of child-bearing potential and male participants whose partner is of child-bearing potential must be willing to ensure that they or their partner use effective contraception during the study
- Participant has clinically acceptable laboratory and ECG at enrolment.
- Negative lateral flow or polymerase chain reaction (PCR) test for SARS-CoV-2
- For healthy volunteers:
 - No clinical history of allergic rhinitis, asthma or eczema
 - Negative skin prick tests or specific IgE response to a panel of common aeroallergens: cat, dog, grass pollen, tree pollen, house dust mite, fungal spores
 - Normal blood eosinophil count (< 300 cells/ μ L)
 - Normal baseline forced expiratory volume (FEV₁) i.e. \geq 80%
- For volunteers with allergic rhinitis with or without asthma:
 - A clinical history of allergic rhinitis symptoms (sneezing, runny or itchy nose) in response to aeroallergens
 - At least one positive skin-prick test or specific IgE response to a panel of common aeroallergens: cat, dog, grass pollen, tree pollen, house dust mite, fungal spores
 - Pre-bronchodilator FEV₁ \geq 50% predicted
 - Participants are permitted to have physician-diagnosed mild to moderate asthma which is not poorly controlled as evidenced by an Asthma Control Questionnaire (ACQ-5) score of \leq 1.5.
 - If they have asthma, they are permitted to be on inhaled corticosteroid (ICS) and a long-acting beta agonist (LABA), but no other controller medication.
- Have had no other courses of medication including nasal and systemic corticosteroids, whether prescribed or over-the-counter, in the four weeks before first study dose other than mild analgesia, vitamins and mineral supplements or, for females, oral contraceptives.

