11. STATISTICS

11.1 Description of Statistical Methods

This is an open label interventional trial to investigate basic mechanisms of innate immunity. The following data outputs will be generated:

- Single-cell transcriptomic signatures
- Epigenetic signatures
- Nasal and blood cytokine levels

This data is typically of a non-parametric distribution and the statistical plan will follow a similar template to the previous publication using R848 challenge (15). For the single-cell and epigenetic datasets, a series of pre-processing quality control checks will take place followed by cell and gene-level downstream analysis with the support of specialised bioinformaticians.

For protein analysis, data will be plotted for individual cytokines using raw data at an individual level. For the repeat R848 challenge, area under curve (AUC) values will be calculated for each cytokine and paired Wilcoxon signed-rank test will be used to compare differences between each challenge with the hypothesis that repeat R848 challenge causes increased responses on secondary challenge.

AUC values of cytokine production after R848 challenge will also be compared between healthy and allergic participants using unpaired Mann-Whitney test.

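### The healthy v allergic comparisons are between unmatched, unadjusted groups, so as planned they cannot separate an allergy difference from age, sex, calendar time, laboratory batch or inhaled steroid use

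*Combined protocol and SAP*

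**What the plan says.** Protocol section 6.2 makes the group contrast the first secondary outcome: "Difference in CXCL10 nasal mucosal gene expression at 24 hours after R848 challenge between healthy subjects and those with allergic rhinitis". It is also the first secondary objective in section 5.2. For cytokine AUC values, section 11.1 states that they "will also be compared between healthy and allergic participants using unpaired Mann-Whitney test". No covariates are named, and no specific test is given for the gene-expression contrast.

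Section 8.2 gives one list of sources for all participants: "Participants in this study will be recruited from Cambridge University Hospital (CUHFT), University of Cambridge, volunteer databases and advertising in the Cambridge area". Within the hospital it then says: "Participants from CUHFT may be recruited from outpatients (in particular departments of allergy and asthma) or comprise of staff working there".

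Section 7.2 admits "Male or female aged 18 years and above", with no upper limit. Of volunteers with asthma, who can only be in the allergic group, it says "they are permitted to be on inhaled corticosteroid (ICS) and a long-acting beta agonist (LABA". Section 6.1 fixes equal numbers of allergic and non-allergic volunteers and balances nothing else. The synopsis gives a study duration of two years, and no section sets a rule on time of year or on allocating samples to laboratory batches.

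The data needed to describe the groups are collected. Section 8.2 lists "Demographics: date of birth, gender, race, smoking and drinking habits" as well as concomitant medication.

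**The concern.** When groups are defined by disease, comparability has to come from recruitment or from analysis. Here neither is specified. Age, sex, month of challenge and assay or sequencing batch can each differ between the groups, and each could plausibly affect nasal CXCL10. Two features make a systematic difference possible, beyond a chance one: a clinic route that would mainly supply allergic volunteers, and steroid and LABA use permitted in one group only.

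Time of year matters by the protocol's own definitions. Allergic volunteers are selected for symptoms on exposure to aeroallergens, the test panel includes grass and tree pollen, and the outcome is measured in the nose.

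At stake is the reading of secondary outcome 1, the AUC group comparison and the exploratory comparison of single-cell and epigenetic profiles. A difference could be credited to allergy when part or all of it comes from the make-up of the groups; a real difference could also be hidden.

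**Working it through.** **Inputs from the protocol.** Up to 12 per group (11.2). First challenge with R848 in 20 volunteers and saline in 4 (8.3). Significance at P < 0.05 (11.3). The plan has no figure of its own to reproduce: 11.2 gives no effect size, SD or power for the group comparison.

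**Assumptions.** The saline recipients are split evenly, which leaves 20/2 = 10 R848 recipients per group (the split is not stated). The test is two-sided (not stated). The Mann-Whitney test is also used for gene expression. CXCL10 is roughly normal on some scale with SD 1.

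**Step 1: is there any control?** Matching: none. Quotas by age or sex: none. Calendar rule: none. Batch rule: none. Covariates in 11.1: none. Shared restrictions do exist: section 7.3 excludes recent infection, smoking in the previous 6 months and significant comorbidity.

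**Step 2: chance imbalance alone.** If both groups came from one population with 50% women, two independent binomials differ by 4 or more women with probability 0.115 (10 v 10) or 0.152 (12 v 12). Mean age differs by at least 0.5 SD with probability 2[1 − Φ(0.5/√(2/n))]: for n = 10, 0.5/0.447 = 1.118, giving 0.264; for n = 12, 0.5/0.408 = 1.225, giving 0.221. Such imbalances are common, but they do not inflate the error rate, because chance imbalance is already part of the sampling variation that the test allows for. Only a systematic difference does so.

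**Step 3: from imbalance to shift.** For a binary factor, the shift in the group difference is b × (p₂ − p₁), where b is the factor's effect on CXCL10 in SD units. A gap of 4 women in 10 (40 percentage points) with an assumed b of 0.5 gives 0.5 × 0.4 = 0.2 SD. To reach 0.5 SD, b would have to be 0.5/0.4 = 1.25 SD. For age, a difference of 0.5 SD with an assumed correlation of 0.3 gives 0.5 × 0.3 = 0.15 SD.

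**Step 4: false-positive rate.** Simulated two-sided Mann-Whitney test, 10 per group, no allergy effect, 100,000 runs per row:

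| Assumed systematic shift (SD) | Rate of P < 0.05 |
|---|---|
| 0 | 4.4% |
| 0.15 | 5.4% |
| 0.2 | 6.2% |
| 0.5 | 16.0% |
| 0.75 | 31.5% |

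A second simulation (20,000 runs per scenario) let a binary factor differ in prevalence between the groups. At 10 per group and b of 0.5 to 1.0 SD, the rate was 6% to 11% for prevalences of 30% v 70%, and 12% to 34% for 10% v 90%. With 50% in both groups it was 4.4%.

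**The case against.** A reader might infer from the clinic sentence that the two groups are drawn from different sources. The text does not say so. Section 8.2 gives one list, names clinics and staff in the same sentence as options, and leaves every other route open to both groups. A source difference is possible but not planned.

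A reader might also conclude that no group difference could ever be attributed to allergy. That is too absolute. The restrictions in 7.3 apply to both groups, most other medication is barred for four weeks, age, sex and medication are recorded, and a mucosal sample is taken at 0 h. The objectives speak of comparing differences and make no causal claim. Nor does the point reach the primary outcome, "Increase in CXCL10 nasal mucosal gene expression at 24 hours after nasal challenge with R848 compared to baseline", which is within person. The two years in the synopsis is the study's duration, so it should not be read as a stated recruitment period.

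It can further be said that pollen-driven inflammation and steroid use are part of what it means to have allergic disease. That is fair. Mixing the groups over the year will not remove a pollen effect that arises mainly in sensitised people, and leaving out ICS users changes which allergic volunteers are studied.

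Finally, moderate assumptions give little inflation (5% to 6%), and the larger rates need large shifts that nothing in the documents supports or rules out.

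All of this limits the point without removing it. The available data are not used in any stated group analysis. Adjustment chosen after the fact is weak and discretionary at 10 to 12 per group. Change from baseline would not remove factors that modify the response to R848.

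**Conclusion.** The point holds for the healthy v allergic comparisons only. As written, the plan neither balances the groups on age, sex, calendar time or batch nor adjusts for them, and it permits ICS/LABA in one group. A significant result would show that the groups differ, without showing that allergy is the reason.

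The size of any bias is unknown. At 10 per group the false-positive rate runs from about 6% (0.2 SD shift) through 16% (0.5 SD) to 32% (0.75 SD), against about 4% with no shift. These figures rest on assumed shifts, an even saline split, a two-sided test and normal data. They show how sensitive the result is; they do not predict a bias. The change is worth making because balance over recruitment and batches cannot be recovered once samples have been taken and run.

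**What to change.** In sections 7.1 and 8.2:
- frequency-match the two groups on sex and broad age band;
- recruit both groups concurrently through the year;
- place samples from both groups in every assay and sequencing batch.

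In section 11.1:
- keep the Mann-Whitney test, and say whether it also applies to the gene-expression contrast;
- add a sensitivity comparison of healthy volunteers with allergic volunteers not on ICS;
- report age, sex, recruitment source and challenge date by group;
- present the contrast as an association.

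Frequency matching is preferable to strict same-month pairs. Pairs would be hard to keep alongside the minimum six-week wait after a screening biopsy, could be broken by the saline allocations, and would not suit an unpaired test.

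The cost is somewhat slower recruitment. The no-ICS subset will be small, so that comparison will be imprecise. No extra participants or procedures are needed, and age, sex and medication are already recorded.

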6. STUDY DESIGN

6.1 Summary of Trial Design

The first stage of the study will include up to 6 participants (healthy or allergic disease) to undergo nasal mucosal tissue and blood collection without any nasal challenge. These samples will be used to optimise the protocols required for downstream processing, e.g. for single cell and epigenetic analysis.

The main component of the study is an open label design employing nasal challenge with a topical spray using saline or a TLR7/8 agonist R848. The aim is to perform deep immunophenotyping of nasal mucosal tissue and peripheral blood before and after nasal challenge with R848 and compare responses between non-allergic and allergic individuals. Some participants will undergo repeat challenge two weeks later with assessment of cytokine, chemokine, and gene expression profiles to determine which cells contribute to innate immune memory of previous exposures and how this may be altered in disease.

After an initial screening visit to determine eligibility, participants constituting equal numbers of non-allergic and allergic individuals will undergo nasal challenge with R848 (n=24). They will have sampling performed for up to 24 hours and can choose to go home or stay overnight in the Cambridge Clinical Research Centre (CCRC). This will be the end of the study for half of the participants.

The remaining half will be invited to subsequently undergo repeat saline (n=2) or R848 (n=10) challenge approximately two weeks later to determine clinical tolerability, assess for exaggerated or dampened nasal mucosal immune responses and investigate mechanisms of innate immune memory, and how they may differ between the groups.

The maximum duration for participants in the study are as follows (Appendix A):

Single challenge study (n=12): one day

Double challenge study (n=12): two days spread two weeks apart

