7.3 Exclusion Criteria

- Recent infections in past 14 days before screening: especially upper respiratory tract illnesses (including colds and influenza), sore throats, sinusitis, infective conjunctivitis.
- Lower respiratory tract infection in past 28 days
- Nasal anatomical defects, precluding use of nasal sampling techniques
- The participant may not enter the study if any of the following apply:
 - Female participants who are pregnant, lactating or planning pregnancy during the study.
 - Respiratory diseases (other than hay fever or asthma where specified)
 - Significant medical history of hepatic, cardiovascular, gastrointestinal, renal, endocrine, infective, haematological, autoimmune, metabolic, rheumatological, neurological, dermatological or neoplastic conditions
 - Extreme obesity (BMI >40)
 - Depression and psychiatric disorders
- Any other significant disease or disorder which, in the opinion of the Investigator, may either put the participants at risk because of participation in the study, or may influence the result of the study, or the participant's ability to participate in the study.
- Participants who have participated in another research study involving an investigational product in the past 12 weeks
- Smoking in previous 6 months

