8.3 Subsequent Assessments

All study visits and procedures are outlined in appendix B – the following details pertain to participants undergoing nasal challenge:

Visit 1 This visit will take place as close to a negative COVID test result. They will undergo a brief medical assessment including baseline physiological observations. They will then undergo nasal lavage followed by nasal curettage/brushing and blood sampling.

Subsequently, nasal challenge with saline (n=4) or R848 (n=20) will then be performed and non-invasive nasosorption samples will be taken every 2 hours until 8 hours after challenge. Physiological observations, total nasal symptom scores (TNSS) and peak nasal inspiratory flow (PNIF) will also be assessed 2-hourly. Blood will be collected for white blood cell differential and serum 4 hours after nasal challenge.

Participants can then choose to go home or have the option of remaining at the CCRC overnight as it has the facilities to provide this support (e.g. if the patient has travelled from further away).

Visit 2 This will take place at 24h with collection of nasosorption, curettage/brushing and a blood sample along with assessment of physiological observations, TNSS and PNIF.

For up to half the group who volunteered for an initial post-nasal space biopsy (6 weeks earlier), a second post-nasal biopsy will be undertaken. For these participants this will be the end of the study.

Visit 3 For the remaining half of the participants (n=12), they will undergo a second nasal challenge with saline (n=2) or R848 (n=10) to investigate mechanisms of innate immune memory in epithelial cells. All assessments and procedures will be identical to visit 1.

Visit 4 All study assessments and procedures will the same as visit 2.

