19. APPENDIX A: STUDY FLOWCHART

20. APPENDIX B: SCHEDULE OF PROCEDURES

Procedures	Visits				
	Screening	Visit 1 (duration 10h) 1 st nasal challenge	Visit 2 (at 24h) 1 st nasal challenge	Visit 3 (duration 10h) 2 nd nasal challenge	Visit 4 (at 24h) 2 nd nasal challenge
Informed consent	X				
Demographics, Medical History and Medications	X				
General physical examination	X				
ECG and Laboratory tests	X				
DNA blood test (up to 8.5mL)	X				
SARS-CoV-2 Lateral Flow or PCR nasal swab		X (negative test prior to nasal sampling)		X (negative test as close as possible to sampling)	
1 st Nasal challenge with saline (n=4) or R848 (n=20)		X			
2 nd Nasal challenge with saline (n=2) or R848 (n=10)				X	
Vital signs, clinical assessment and symptom scores		X (2 hourly)	X	X (2 hourly)	X
TNSS and PNIF		X (2 hourly)	X	X (2 hourly)	X
Nasal lavage		X (0h)		X (0h)	
Nasosorption (filter strips to absorb mucosal fluid)		X (15min, 30min, 1hr, 2hr, then 2 hourly)	X	X (15min, 30min, 1hr, 2hr, then 2 hourly)	X
Nasal curettage	X	X	X	X	X
Nasal brushing	X	X	X	X	X
Post-nasal space biopsy (a minimum of 6 weeks prior to challenge) and at visit 2	X		X		
Blood (9ml FBC, serum 0h, 4h, 24h), (13ml single cell analysis and Truculture at 0h and 24h)		X (0h and 4h)	X	X (0h and 4h)	X

TNSS Total Nasal Symptom Score; PNIF Peak Nasal Inspiratory Flow

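### Pregnancy is tested only at screening, so the result is at least 6 weeks old for up to 10 first R848 doses and at least about 2 weeks old for the 10 second doses

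*Combined protocol and SAP*

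**What the plan says.** Section 7.3 excludes "Female participants who are pregnant, lactating or planning pregnancy during the study". Section 7.2 adds that women of child-bearing potential, and men whose partners are, "must be willing to ensure that they or their partner use effective contraception during the study".

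The pregnancy test appears once, among the screening laboratory tests in section 8.2: "Biochemistry, full blood count, liver function test, total IgE, skin prick allergy testing, pregnancy test (for women) will be performed". In Appendix B the row "ECG and Laboratory tests" is marked at Screening and at no later visit, and there is no separate pregnancy-test row.

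For Visit 1, section 8.3 says of participants before challenge: "They will undergo a brief medical assessment including baseline physiological observations". It then lists lavage, nasal sampling and blood sampling. Visit 3 repeats Visit 1. Neither mentions pregnancy.

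Two parts of the design put a known delay between screening and an R848 dose:

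- **Biopsy volunteers** (section 8). The first biopsy is taken at the screening visit, followed by "a minimum of 6-weeks (to ensure wound healing) before performing nasal challenge with saline (up to n=2) or R848 (up to n=10"). Of this group the section says: "These participants will only undergo a single nasal challenge and not the second repeat challenge".
- **Double-challenge participants** (section 6.1). They are invited to "subsequently undergo repeat saline (n=2) or R848 (n=10) challenge approximately two weeks later".

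**The concern.** Pregnancy status can change between screening and dosing, and the protocol requires or permits weeks between the two. A woman who tests negative at screening and then conceives could receive R848 with every scheduled check completed. The exclusion exists to prevent this.

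The protocol already re-checks one status that changes over time: Appendix B requires a negative SARS-CoV-2 test at both Visit 1 and Visit 3. Pregnancy has no equivalent.

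What is at stake is participant safety in a study of basic mechanisms, where section 11.1 claims no therapeutic purpose for the challenge. The documents give no pregnancy or fetal data for R848, reassuring or otherwise. No endpoint, sample size or analysis depends on this point.

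**Working it through.** The plan states no figure for the age of the test at dosing, so there is none to reproduce. It follows from the visit schedule.

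**Inputs**

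- Pregnancy test: screening visit only (section 8.2, Appendix B).
- First challenges: 20 R848 and 4 saline (section 8.3, Appendix B). Section 6.1 describes all 24 as R848; the more detailed split is used here.
- Biopsy group: up to 10 R848 and up to 2 saline, at least 6 weeks after screening, with no second challenge (section 8).
- Second challenges: 10 R848 and 2 saline, about two weeks after the first (section 6.1).
- Screening to Visit 1 in participants without biopsy: not stated. Call it x days, x ≥ 0.

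**Count check.** R848: 10 biopsy + 10 double-challenge = 20. Saline: 2 + 2 = 4. Both agree with Visit 1. The two groups do not overlap.

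**Age of the test at each R848 dose**

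Age = (screening to Visit 1) + (Visit 1 to Visit 3, if a second dose)

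| R848 dose | Number | Age of test |
|---|---|---|
| First dose, biopsy volunteers | up to 10 | ≥ 6 × 7 = 42 days, no maximum |
| Second dose | 10 | about 2 × 7 + x = 14 + x days, so at least about 14 |
| Other first doses | at least 20 − 10 = 10 | x days, not limited |

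Total R848 doses: 20 + 10 = 30. A minimum delay is documented for up to 10 + 10 = 20 of them, one dose in each of up to 20 participants.

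**How many could concern women.** The documents give no sex split. As an assumption, if women of child-bearing potential make up 25%, 50% or 75% of recipients, then up to 20 × 0.25 = 5, 20 × 0.50 = 10 or 20 × 0.75 = 15 of these doses go to women with a test that old. These numbers count old tests; they do not count pregnancies.

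**Size of the risk (illustration).** Take the 50% case, 5 biopsy women at 6 weeks and 5 double-challenge women at 2 weeks, and assume contraceptive failure of 1% to 10% a year. Woman-years between test and dose: 5 × 6/52 + 5 × 2/52 = 40/52 = 0.77. Expected pregnancies starting in that time: 0.77 × 0.01 ≈ 0.008 to 0.77 × 0.10 ≈ 0.08 for the whole trial. Both intervals are minimums, and longer gaps raise the figure in proportion.

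**The case against.** The strongest reply is that pregnancy is listed in section 7.3 as a bar to entry and is tested at entry. After entry the protocol relies on other controls: effective contraception, exclusion of women planning pregnancy, a medical assessment before each challenge, and the investigator's power under section 8.5 to discontinue someone who becomes ineligible. On this view a repeat test is an extra layer, and its absence contradicts nothing in the text. The expected number of pregnancies is far below one. Section 4 also reports that low-dose intranasal R848 changed neither physiological measures nor serum inflammatory mediators compared with saline.

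Much of this stands. The risk is small, harm has not been shown, and biopsy is optional, so the group with the 42-day minimum could be smaller than 10 or empty.

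It does not remove the gap. Contraception lowers the chance of pregnancy but detects nothing, and it can fail in someone who follows the protocol fully. The content of the pre-challenge assessment is not itemised. It may include a question about pregnancy, but a question cannot find a pregnancy the participant does not know of. Discontinuation works only once the pregnancy is known. The tolerability data describe the volunteers themselves and say nothing about a fetus.

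One limit on the check: the Appendix A flowchart was not available. Section 8.3 refers the reader to Appendix B for visits and procedures, and Appendix B has no repeat test.

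**Conclusion.** The concern holds. As written, the protocol can be followed exactly and still allow R848 to be given during an undetected pregnancy. The documented minimum age of the test is 42 days for up to 10 first doses and about 14 days for the 10 second doses. No dose has a documented maximum.

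The timing and the counts come directly from the text. The number of women affected does not: 20 doses is an upper bound that includes men, and the 25% to 75% shares and the contraceptive failure rates are assumptions. The absolute risk is low. The change is worth making because it enforces an exclusion the protocol already sets, at very little cost.

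**What to change.** Add a urine pregnancy test for women of child-bearing potential at Visit 1 and Visit 3, with a negative result recorded before the nasal challenge is given. Put it in the section 8.3 visit descriptions and as a new row in Appendix B. The age of the test at every R848 dose then falls to about 0 days, including the first doses whose screening interval is unspecified.

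The cost is one dipstick per woman of child-bearing potential with a single challenge and two with a double challenge, at visits already held. No extra visit, staff or invasive procedure is needed. The change looks like a minor amendment, but under section 14.2 its classification follows the ethics committee's definitions, and the participant information may need a line about the added test.
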